Power wheelchairs (PWCs) offer children who are unable to independently opportunities for participation in social, educational, and leisure activities. Unfortunately, children who have severe cognitive, motor, or sensory impairments may need extended training to be able to master the PWC skills needed to "qualify" for their own PWC. To address this need, a PWC training system called the KWIC Trainer was developed. The KWIC Trainer used a platformbased design to temporarily convert a manual wheelchair into a powered wheelchair, thereby allowing children to remain in their own manual wheelchair and use their own custom seating system during training. To increase motivation to train, a videogaming mode allowed children to play videogames shown on a TV screen using the KWIC Trainer joystick. During videogames, the KWIC Trainer could be configured to both rotate the KWIC Trainer in place and translate it a small distance, thereby progressively teaching children the concept that moving the joystick resulted in movement of their wheelchair. In a pilot project, the KWIC Trainer showed promising results, allowing 2 out of 8 children with CP who had been previously excluded from power mobility training to gain the skills needed to qualify for purchase of their own PWC. Despite this initial success, the KWIC Trainer was bulky, had limited ground clearance, and took a long time to set up, which made it difficult to use in a real-world environment. To address these concerns, a new PWC training system, called the IndieTrainer, will be developed as part of a Small Business Innovation Research Grant (SBIR). The IndieTrainer will build upon both the KWIC Trainer and the indieGoTM, a mobile platform device that also temporarily converts a child's manual wheelchair into a PWC (see section 8). The IndieTrainer will be a game-based training program that will allow licensed physical and occupational therapists to progress children throughout the continuum of learning to use a PWC. As part of the SBIR, GVSU will be contracted to conduct an open-label, single-arm clinical trial to evaluate use of the IndieTrainer to improve a child's PWC skills. This proposal outlines this study.

1c. Study Location(s)

Indicate the primary site at which the research will be conducted.

Site: Grand Valley State University

1d. Project Timeline
Anticipated Start Date:
06/01/2021
Anticipated End Date:
05/31/2024

2. Protocol Personnel
 [name]
 [name]
 3. Review Type
 3. Level of Review
 What type of review do you believe your project falls under?
 Expedited
 6. Subject Population
 6a. Subject Population Description
 6a(i). Number of Subjects

6a(ii). Subject Population Characteristics

Briefly describe the subject population characteristics (i.e., age ranges, and where appropriate, gender, ethnic background, and health status).

Participants will be children (defined as 3 to <21 years of age) with cerebral palsy or other similar conditions who have mobility limitations (e.g., function at Gross Motor Function Classification System Level IV or V), are unable to functionally self-propel a manual wheelchair, and who do not have an individually prescribed powered wheelchair. Other inclusion criteria include: parent report that the child has beginning cause and effect skills (e.g. the child responds to games such as peek-a-boo or activates toys through motor activities such as pressing, hitting, batting, or squeezing), age =5 years and <21 years old, child currently uses a manual wheelchair or adaptive stroller that can be safely used with the IndieTrainer system (i.e. functioning wheel brakes to remain locked onto platform, etc.), and the ability to attend to visual stimuli as assessed by [name] (to ensure that the child was able to attend to the videogame activities) as assessed by [name]. Exclusion criteria include any condition or issue that would prevent a child from safely using the IndieTrainer system as determined by [name]. The child and his/her wheelchair combined must also weigh <300 pounds to safely use the IndieTrainer.

6a(iii). Number of Subjects Justification

Provide a justification for why the number of subjects to be recruited is appropriate.

A sample size of 25 child-parent dyads was determined using an estimated effect size (Cohen's d) of 1.48 for T0 to T1 changes in the primary outcome measure, a significant within group difference at alpha = 0.05 with a 90% probability, and a 10% dropout/attrition rate, as based on our previous work.

6b. Vulnerable Populations

Will any vulnerable populations be recruited for this study? These include, but are not limited to, children under the age of 18, prisoners, mentally disabled persons, economically disadvantaged, or pregnant persons.

Yes

6b(i). Vulnerable Population Justification

Indicate the vulnerable population(s) to be recruited.

Children under the age of 18

Enter a justification for recruiting the vulnerable population(s) identified above. If you selected "Other," please describe.

Given that the IndieTrainer system is focused on improving PWCs in children who have severe motor and other impairments, the IndieTrainer system must be assessed for use with children. Project procedures will not be initiated without assent from any child who can provide assent and who is 7 years of age or over. Given that many of children in this may not have the motor ability to sign their own names, we will be requesting an alteration in signed assent as outlined later in this document. It must also be noted that not all children who may be involved in the study will have the ability to indicate "yes" or "no". Such children, even if 7 years of age or older, would not be capable of providing assent. Nonetheless, study procedures will be explained to all participants, even if they are not capable of providing assent. This will be done as a matter of respect. Given that the participants may not be able to communicate with the researchers or their families, all research activities will be discontinued if a participant demonstrates signs that he/she does not want to participate in the activity (crying for more than 2 minutes, etc.).

7. Subject Recruitment and Consent

7a. Recruitment and Selection of Subjects

7a(i). Recruitment Process

Briefly describe how participants will be recruited.

A non-probability, convenience sampling plan was used to recruit child-parent participant dyads. Specific recruitment techniques included posting virtual fliers on relevant websites, sharing virtual fliers via social media sites and platforms, and emailing fliers to local agencies, clinics, and professionals involved in the provision of medical, rehabilitation, or educational services for children with CP or other similar conditions.

7a(ii). Inclusion/Exclusion Criteria

Describe the criteria you will use to determine which subjects will be included and which excluded.

Inclusion criteria:

- 1. Age 3 years to <21 years old
- 2. Have a diagnosis of cerebral palsy or other similar condition
- 3. Be unable to walk effectively (As determined by [name], a licensed physical therapist)
- 4. Unable to functionally self-propel a manual wheelchair (As determined by [name], a licensed physical therapist)
- 5. Do not have an individually prescribed powered wheelchair
- 6. Parent report that the child has beginning cause and effect skills (e.g. the child responds to games such as peek-a-boo or activates toys through motor actions such as pressing, hitting, batting, or squeezing)
- 7. Currently uses a manual wheelchair or adaptive stroller that can be safely used with the IndieTrainer system (i.e. functioning wheel brakes to remain locked onto platform, etc.) as

assessed by [name]

8. Has the ability to attend to individually motivating visual stimuli for 5 seconds as assessed by [name] (to ensure that the child was able to attend to the videogame activities). Exclusion criteria include any condition or issue that would prevent a child from safely using the IndieTrainer system as determined by [name].

In addition, at least one parent or guardian must converse in English for their child to participate

in the study.

Given that many children in the target population are often non-verbal and unable to indicate "yes" or "no", to ensure child safety, the researchers will need input from the parent about if their child's response to research activities is typical for their child. The child and his/her

wheelchair combined must also weigh <300 pounds to safely use the IndieTrainer. [name] will use the Eligibility Assessment form uploaded in text box 7a(iv) to assess all inclusion and exclusion criteria prior to the onset of any data collection activities.

7a(iii). Researcher/Subject Relationship None

7c. Consent/Assent Process Description

7c(i). Consent/Assent Description

Provide a description of the process for obtaining consent/assent of the subjects or their representatives.

[name] will review study procedures and criteria privately with each family and make sure that any questions the family may have been answered. A parent will sign the consent/permission form only if he/she freely chooses to do so. If obtaining assent is applicable for the potential participant, [name] will obtain ethically appropriate assent as outlined in the assent process. [name] will also use the Eligibility Assessment form to assess all inclusion and exclusion criteria prior to the onset of any data collection activities.

For participants 18 to <21 years of age who are their own guardian, [name] will review study procedures and criteria privately with each potential participant and make sure that any questions the potential participant may have been answered. A participant 18 to <21 years of age consent to participate in the study only if he/she freely chooses to do so.

Ensuring Voluntary Participation

How will you ensure that the voluntary nature of participation is apparent to the subjects?

This is clearly outlined in the consent/permission form and in the assent process for children who can provide assent.

7c(v). Participant Withdrawal

How will you ensure that a subject can freely withdraw from the research aspects of

the study without concern about being penalized?

This is clearly outlined in the consent/permission form and in the assent process for children who can provide assent.

7c(vi). Consent Waiver/Alteration
Are you requesting a waiver or alteration of informed consent?
Yes

In order to be granted a waiver or alteration to informed consent, the federal regulations require additional criteria be met. The questions below will enable you to provide information to address these additional criteria.

Describe the waiver or alteration being requested.

For all child participants <18 years of age and for participants who are 18 to <21 years of age who are not their own guardian, the researchers request an alteration of assent and would like to request that verbal assent be obtained rather than signed assent. Many of children in this population may not have the motor ability to sign their own names. Children who are unable to physically sign their name may be embarrassed or may feel uncomfortable when asked if they are physically able to sign their name. Obtaining verbal assent will avoid having to ask the child if he/she is physically able to sign his/her name. Verbal assent will be documented on the assent

form.

Participants 18 to <21 years of age who are their own guardian may not have the motor ability to sign their own names. Therefore, if a participant is 18 to <21 years of age and his/her own guardian and is unable to physically sign his/her name, the researchers request an alteration of consent and would like to request that verbal consent be obtained rather than signed consent. Verbal consent will be documented on the consent form.

Additional Criteria: Minimal Risk Explanation

Explain how the research involves no more than minimal risk to the participants.

Standard of Care: Before discussing risks in this study, it is important for reviewers to have an understanding of the standard of care in the area of power mobility training. [name] has frequently provided power mobility training for children during her 30+ years of practice as pediatric physical therapist. The standard of care in this area is for therapists to obtain a standard power wheelchair (either from a wheelchair vendor or perhaps through donation or by borrowing one from a child who already has one) and use pillows, towels, etc. to temporarily modify the standard power wheelchair to accommodate a specific child as much as possible. Since a standard power wheelchair is not customized to the needs of the child trialing the device, the standard power wheelchair may or may not fit the child and may or may not adequately and safely position the child. During power mobility training, the therapist walks along-side the child while the child is practicing driving and if the child comes upon a dangerous situation or needs to stop moving the power wheelchair, the therapist simply removes the child's hand from the access device - either a joystick or switch(es). A standard power wheelchair does not have an attendant control or emergency stop buttons.

Power Mobility Training in the IndieTrainer: The IndieTrainer is intended only for use under the supervision of a licensed physical or occupational therapist as part of a power mobility-training program. Multiple safety features have been included in the design of the IndieTrainer to ensure user safety while at the same time allowing users to access, explore, and learn from their environment. A child's manual wheelchair is securely attached to the IndieTrainer platform using methods similar to those that secure a wheelchair in a school bus or van during transport. This allows the child to be optimally and safely positioned in their manual wheelchair with their own customized seating system while practicing power mobility skills. When safety or environmental factors necessitate that the therapist take total control of the IndieTrainer, an attendant control allows the therapist to override all drive functions and assume full operational control of the IndieTrainer. Emergency stop buttons are also provided to ensure safety. The driving speed of the IndieTrainer is set by the therapist and can be set to meet the needs of the individual driving to ensure that users are not going too fast.

Given the data storage methods used in the study (and outlined later in this document), the risk of a data breach is minimal. Should a breach occur, information about a child's power mobility skill is not of a highly sensitive nature.

Additional Criteria: Rights and Welfare of the Participants

Explain why the waiver or alteration will not adversely affect the rights and welfare of the participants.

All participants will undergo the same consent and permission process. For children 7 years of age or over who can partake assent process, the assent process will be the same. The only difference relates to whether the consent or permission or assent form is signed. All participants will still receive a copy of the appropriate consent/permission or consent form.

Additional Criteria: Practicality of Conducting the Research Explain why the research could not be practicably carried out without the waiver or alteration.

Many of children in this population may not have the motor ability to sign their own names. Children who are unable to physically sign their name may be embarrassed or may feel uncomfortable when asked if they are physically able to sign their name. Obtaining verbal assent

(defined as whatever communication system the child uses) will avoid having to ask the child if he/she is physically able to sign his/her name. Verbal assent will be documented on the assent form.

Many participants 18 to <21 years of age who are their own guardians may have the motor ability to sign their own names. Therefore, if a participant is 18 to <21 years of age and his/her own guardian and is unable to physically sign his/her name, the researchers request an alteration of consent and would like to request that verbal consent be obtained rather than signed consent. Verbal consent will be documented on the consent form.

Additional Criteria: Additional Information to Participants

Whenever appropriate, the participants will be provided with additional pertinent information after participation. Explain how this will be accomplished or why this cannot be done.

All information related to the study will be provided to all participants prior to the onset of any data gathering activities.

Additional Criteria: Identifiable Private Information/Biospecimens Does this research involve identifiable private information or identifiable biospecimens?

No

- 8. Research Procedures and Methods
- 8. Research Procedures and Methods
- 8a. Frequency and Time Involvement

Describe the frequency and length of time subjects will be involved in the study.

The focused physical therapy examination will take 90-120 minutes. Each training session will take approximately 60 minutes. An additional 30-45 minutes will be added to the final training session. The single follow-up session will take 45-60 minutes. The total time involved in the study is between 8 hours, 45 minutes and 12 hours, 45 minutes.

8b. Description of Intervention/Data Collection

Describe step-by-step what will occur during your project, including any intervention(s). Include a description of the data you are collecting (i.e., the specific variables, the specific tests/surveys, data collection instruments, etc.), how it will be collected, and how it will be analyzed.

Research Design: The research design to be employed in the proposed is a single-arm, open label study without a control group involving the following components: (a) Baseline examination and baseline/pre-intervention testing (T0); (b) A three-week intervention period consisting of two, 60-minute PWC skills training sessions per week; (c) Post-intervention testing completed immediately after the completion of the intervention period (T1); and (d) A single session retention trial held 4 weeks after the completion of the intervention period (T2).

Prior to the onset of any data collection activities, [name] will obtain ethically valid consent, permission, and assent as appropriate using the procedures previously outlined in this document.

Prior to the onset of data collection, [name] as a licensed physical therapist will perform a focused physical therapy examination to determine whether the participant would best be able to drive using a joystick or switch(es) as well as how and where the joystick or switch(es) should be placed to best accommodate each participant's needs. Per the standards of the physical therapy profession, this examination will include obtaining a complete medical history via parental interview (this interview will not be recorded) and a systems review (including a screen of cardiopulmonary, integumentary, musculoskeletal, and neurological systems). Obtaining a complete medical history and completing the review of systems for each potential participant

will allow [name] to determine if it is safe for each potential participant to partake in power mobility training. The switches or joystick used will be placed on each participant's manual wheelchair only when he or she is driving and will not result in any permanent changes to the participant's manual wheelchair.

TO data collection activities will also take place during this focused physical therapy evaluation. A demographic form will be completed. The primary outcome measure will be the Assessment of Learning Powered mobility use (ALP), a process-based assessment instrument reflecting the process of understanding how to use a PWC. Secondary outcome measures pertaining to PWC skill execution included the Wheelchair Skills Checklist (WSC) and the Canadian Occupational Performance Measure (COPM). A focused, two question parent/caregiver interview will be conducted and digitally recorded. The interview questions will be: 1) Can you describe (your child's name) for me?; and 2) How do you think your child will respond to power mobility training? Follow-up prompts to these two main questions will include the parent's perceived benefits and challenges of power mobility training for his/her child. Once parent-report data collection activities are completed, participant's power mobility skills will be assessed by [name], a licensed physical therapist. The child will use the IndieTrainer during administration of the ALP and the WSC.

Participants will then partake in 2 training sessions per week over a 3-week period. NOTE: Should training sessions be cancelled due to child illness or inclement weather, missed training sessions will be rescheduled during the 3-week period. If this cannot be accomplished, the 3-week time period will be extended for up to 7 days. This 7-day extension would only be used when necessary to ensure the child's health, well-being, and safety.

A parent or guardian must accompany the child participant to each training session. Participants will be video-taped and photographed while using the IndieTrainer. These photographs and videos will allow the licensed physical therapist researcher ([name]) to determine how each participant is responding to the IndieTrainer program and will help he licensed physical therapist researcher ([name]) to determine when to progress a participant to the next stage of IndieTrainer program. As noted in the consent/permission form, the GVSU research team may ask permission to use photographs or videos in professional presentations or publications. In such instances, permission (and assent if applicable) would be obtained via a separate Video and Photography Release Authorization Form.

After completion of the final session, T1 testing will occur and will include re-administration of the ALP, the WSC, and the COPM. A focused, two question parent/caregiver interview will be conducted and digitally recorded. The interview questions will be: 1) Can you describe (your child's name) for me? How do you think your child responded to power mobility training? Follow-up prompts to these two main questions will include the parent's perceived benefits and challenges of power mobility training for his/her child. In addition, parents' impressions of the IndieTrainer system will be gathered using the Client Satisfaction Questionnaire (CSQ-8).

T2 testing will involve administration of the ALP and the WSC.

Data Analysis:

Frequency counts will be used to report categorical demographic variables. We will use SAS Studio 5.1 (SAS Institute Inc., Cary, NC, USA) to calculate descriptive statistics for continuous demographic variables and CSQ-8 total scores and to perform all statistical analyses. If appropriate, we will use parametric tests in our analyses. We will use a one-way repeated measures ANOVA to assess differences in ALP and WSC scores at T0, T1, and T2 at 0.05 α level. Post-hoc paired samples two-tailed t-test with a Bonferroni correction will be used as appropriate to assess mean differences between T0 and T1, T0 and T2, and T1-T2. Mean COPM Performance and Satisfaction scores will be assessed via a paired samples two-tailed t-test at 0.05 α level. Frequency counts for total CSQ-8 scores will be reported. The clinical significance of changes between T0 and T1 will be assessed using the following guidelines: an improvement of at least one ALP phase and an increase of ≥2 points in COPM performance. Cohen's d effect sizes will be interpreted as small = 0.20 to 0.49; moderate = 0.50 to 0.79; and large ≥0.80.

Data from the parent/guardian interviews will be transcribed verbatim by the researchers. Qualitative data will be analyzed using the Linguistic Inquiry and Word Count program (LIWC 2015), a text analysis program. LIWC 2015 examines each word in a transcript against an internal dictionary of 6,000+ words to place each word into appropriate linguistic and psychological categories and can objectively evaluate a transcript based on 4 summary language

variables: Analytical Thinking, Clout, Authenticity, and Emotional Tone.

8c. Compensation

Will subjects be compensated for their participation in the study?
No

8d. Deception and Incomplete Disclosure Does this study involve the use of deception?

8h. Contribution to Existing Knowledge Base

How will the resulting information contribute to the existing knowledge base?

The IndieTrainer will be the first power mobility training system specifically designed to optimize

the training process, accommodate varying levels of cognitive capacity and motor impairment, and improve access to power mobility training for the thousands of children with cerebral palsy who are currently excluded from such training and therefore denied the opportunity to independently move and explore.

8i. Dissemination of Results

How will the results be disseminated (presented or published) to the public, scientific community, and research participants?

Findings will be presented at national and international conferences and submitted for

publication in a peer-reviewed journal.

- 9. Personal Identifiable Information
- 9. Personal Identifiable Information

9a. Use of Personal Identifiable Information

Will personal identifiable information and/or protected health information be collected and/or accessed during this study? This can include, but is not limited to: names, phone numbers, email addresses, medical information, educational record data, etc.

Yes

Select the type of personal identifiable information being collected/accessed. (Check all that apply.)

Names

Telephone numbers

Electronic mail (E-mail) addresses

Full face photographic images and any comparable images

For further information regarding data storage and transfer

recommendations/requirements, please consult IRB Guidance G-16: Guidance on Data Management Requirements for Research Data.

9b. Data Acquisition

How will the personally identifiable data initially be obtained?

Each participant will be assigned a unique participant identification number that does not include any identifiable information. The participant ID code will instead reflect the research study: IndieTrainer-(number) - for example: IndieTrainer- 04. [name] will retain a participant key in a locked draw in her locked office. This key will be stored separately from any data or other participant information (demographic forms, etc.). Only [name] will have access to this key.

Interviews with parents will be audio-recorded. As soon as possible after the interview, the audio recording will be stored in a secure method (on encrypted jump drive or as an encrypted file) and the interview erased from the digital recorder. The audio recordings will be transcribed by the researchers. Once this the interview is transcribed, the secure file of the audio recording will be deleted.

Participants will be video-taped and photographed while using the IndieTrainer. As noted in the consent/permission form, the GVSU research team may ask permission to use photographs or videos in professional presentations or publications. In such instances, permission (and assent if applicable) would be obtained via a separate Video and Photography Release Authorization Form.

9c. Access to Personal Identifiable Information

Describe who will have access to the data.

Only [name] will have access to the participant key. GVSU researchers will transcribe the interviews. Only [name] will have access to the photographs and videos - however she may view these with other GVSU researchers to determine how a participant is responding to the IndieTrainer.

9d. Data Storage/Destruction

Where and how will the data be stored?

Contact information will not be stored. The participant key will be stored in a locked draw in [name] locked office. This key will be stored separately from any data or other participant information (demographic forms, etc.). As soon as possible after an interview, the audio recording will be stored in a secure method (on encrypted jump drive or as an encrypted file) and the interview erased from the digital recorder. The audio recordings will be transcribed by the researchers. Once this the interview is transcribed, the secure file of the audio recording will

be deleted. As soon as possible after photographs and videos are obtained, they will be stored in a secure method (on an encrypted jump drive) and deleted from the camera.

9e. Data Destruction

For how long will subjects' identifying information be linked to the data and how will the data be destroyed?

As soon as possible after an interview, the audio recording will be stored in a secure method (on

encrypted jump drive or as an encrypted file) and the interview erased from the digital recorder.

The audio recordings will be transcribed by the researchers. Once this the interview is transcribed, the secure file of the audio recording will be deleted. As soon as possible after photographs and videos are obtained, they will be stored in a secure method (on an encrypted jump drive) and deleted from the camera.

9g. HIPAA Authorization Form

9h. HIPAA Waiver

If you wish to use HIPAA- and/or FERPA-covered data for research purposes, you must either obtain consent from the individual whose data you will be collecting/using, or in the case of HIPAA-covered data, the IRB must approve a HIPAA waiver. FERPA waivers are not available. Are you requesting a waiver or alteration of HIPAA authorization for this study?

10. Risks and Benefits

10a. Potential Risks and Discomforts

10a(i). Nature/Likelihood of Risks

Describe the nature and likelihood of risks to subjects and procedures to minimize risks. Include data breach as a potential risk and indicate what potential effects a data breach might have on the subjects.

10a(ii). Risk Response

Electronic data will be collected and/or stored for this research study. As with any electronic data storage, there is a minimal risk that your data could be lost or stolen. Some children may feel anxious or frustrated when learning to drive in a PWC.

Should an identified risk event occur, specifically, what action(s) will be taken? Any and all adverse events would be reported per GVSU and NIH policies.

10b. Potential Benefits
10b(i). Potential Benefits to Society

Describe the potential benefits to society (e.g., people, academic field, etc.).

The IndieTrainer will be the first power mobility training system specifically designed to optimize the training process, accommodate varying levels of cognitive capacity and motor impairment, and improve access to power mobility training for the thousands of children with cerebral palsy who are currently excluded from such training and therefore denied the opportunity to independently move and explore.

10b(ii). Potential Benefits - Subjects

Are the subjects likely to directly benefit by participating in this study?

Perhaps

10b(iii). Benefit Justification - Subjects

Describe the potential benefits to the subjects and justify why it is likely the subjects will receive these benefits.

Although participants' power mobility skills may improve because of participation in the study, it is not known if participants will benefit from using the IndieTrainer system. This is clearly stated on the consent/permission form.

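### The sample size of 25 cannot be reproduced from its stated within-group inputs: the planned paired t-test needs 8 to 18 enrolled

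*Combined protocol and SAP*

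**What the plan says.** Section 6a(iii) is the only place where the number of participants is justified. It reads: "A sample size of 25 child-parent dyads was determined using an estimated effect size (Cohen's d) of 1.48 for T0 to T1 changes". The effect size refers to the primary outcome, and the remaining inputs are given as "a significant within group difference at alpha = 0.05 with a 90% probability, and a 10% dropout/attrition rate". The effect size and attrition rate are attributed to the team's previous work. The section names no test, sidedness, T0-T1 correlation or number of completers. It also does not say which SD was used to standardise 1.48.

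The design and analysis appear in section 8b. The trial is a "single-arm, open label study without a control group". The primary outcome, the ALP, is analysed by a "one-way repeated measures ANOVA to assess differences in ALP and WSC scores at T0, T1, and T2" at the 0.05 level. After that, "Post-hoc paired samples two-tailed t-test with a Bonferroni correction will be used as appropriate to assess mean differences between T0 and T1", and likewise between T0 and T2 and between T1 and T2, which makes three contrasts. A general condition applies: "If appropriate, we will use parametric tests in our analyses". No non-parametric alternative is named.

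**The concern.** A standardised within-child change of 1.48 is very large, and a paired test detects a change of that size with few children. Twenty-five looked too many for 90% power at that effect. The question was whether any reasonable reading of the stated inputs leads to 25.

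The stakes are limited. Too large a number does not threaten the validity of the test or the estimate. But the section exists to justify how many children are recruited, and a reader takes from it that 25 children give 90% power at d = 1.48. If that is not what the design delivers, the calculation cannot be checked, and a non-significant result would be judged against the wrong detectable effect.

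**Working it through.** **Inputs.** From 6a(iii): d = 1.48, alpha = 0.05, power 0.90, attrition 10%, stated N = 25. From 8b Data Analysis: two-sided paired t-test, with Bonferroni over three contrasts giving 0.05/3 = 0.0167. Assumed because the documents are silent: the SD behind d, the T0-T1 correlation r, and equal SDs at T0 and T1.

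**Method.** Power is 1 - F(t_crit) + F(-t_crit), where F is the noncentral t distribution with n - 1 degrees of freedom and noncentrality dz × √n. Here dz is the mean change divided by the SD of the change. Take the smallest n with power of at least 0.90, then enrolled = n/0.9, rounded up.

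**Reading 1: d is scaled by the SD of the change (dz = 1.48).**
- Alpha 0.05: n = 6 gives power 0.823 and n = 7 gives 0.900; 7/0.9 = 7.8, so 8 enrolled.
- Alpha 0.05/3: n = 9 gives 0.888 and n = 10 gives 0.933; 10/0.9 = 11.1, so 12 enrolled.

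**Reading 2: d is scaled by the single-time-point SD.** Then dz = 1.48/√(2(1 - r)).

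| r | dz | Completers / enrolled, alpha 0.05 | Completers / enrolled, alpha 0.05/3 |
|---|---|---|---|
| 0 | 1.047 | 12 / 14 | 16 / 18 |
| 0.3 | 1.251 | 9 / 10 | 12 / 14 |
| 0.5 | 1.480 | 7 / 8 | 10 / 12 |
| 0.7 | 1.911 | 6 / 7 | 7 / 8 |

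The requirement falls as r rises, so the r = 0 row is the maximum for non-negative correlation. Against 25, the ratios run from 25/18 = 1.4 to 25/8 = 3.1 across the readings 8, 12, 14 and 18.

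**Other analyses that 8b allows.**
- Repeated measures ANOVA: three time points, alpha 0.05, sphericity assumed, noncentrality 3nf²/(1 - r). With the T2 mean at the T1 level or back at baseline, f = 1.48√2/3 = 0.698; with T2 halfway, f = 1.48/√6 = 0.604. Enrolled: 7 or 9 if d uses the SD of the change (equivalent to r = 0.5), and 13 or 16 if it uses the single-time-point SD with r = 0.
- Wilcoxon signed-rank test, one possible fallback: exact critical values, 20,000 simulated normal samples. Enrolled at 0.05 and 0.05/3: 9 and 13 (SD of change), 15 and 19 (single-time-point SD, r = 0).

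**What does give 25.**
- An independent two-group t-test at two-sided 0.05: 10 per group gives power 0.879 and 11 per group gives 0.910; 22/0.9 = 24.4, so 25. This may be the source, but the documents name no formula.
- A paired t-test with r = -1 at alpha 0.05, or with r of about -0.5 at 0.05/3 (22 completers, 25 enrolled).
- A sign test, which the plan does not mention, gives 14 to 28 depending on the SD and alpha, so its range includes 25.

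**What 25 enrolled delivers.** 25 × 0.9 = 22.5, taken as 22 completers.
- Power at 1.48: above 0.999 at either alpha (SD of change); 0.997 at 0.05 and 0.985 at 0.05/3 (single-time-point SD, r = 0).
- Mean change detectable with 90% power: 0.725 SD of the change at 0.05, and 0.842 at 0.05/3.
- On the single-time-point scale with r = 0, multiply by √2: 0.725 × 1.414 = 1.03 and 0.842 × 1.414 = 1.19.

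**The case against.** The strongest reply is that 6a(iii) names no test, so the mismatch is shown only for tests the reader supplies. Section 8b makes parametric tests conditional and names no fallback. A signed-rank test under its least favourable efficiency (0.864), with r = 0 and Bonferroni, needs 22, and a sign test can need 28. The team may also hold a derivation from its previous work that is simply not written down.

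Part of this stands. The bounds of 14 and 18 hold only for the paired t-test with r of zero or more, and the two-group match is inference, not evidence of a wrong formula. But 8b names the paired t-test for the T0-T1 contrast, and 6a(iii) states alpha 0.05 and a within-group difference. The worst signed-rank case still falls short of 25. A negative correlation as strong as -0.5 between repeated scores on the same child is implausible.

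A second reply is that the harm is small. Section 8b interprets results through effect-size bands and clinical thresholds, not through 1.48. If 1.48 uses the single-time-point SD with r = 0, the comparison is 1.48 against 1.03, not against 0.73. This is fair: the gap depends on a scale the documents do not give. It narrows the gap but does not close it, and it is a further reason to state the scale.

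**Conclusion.** The concern holds. With the test that the plan names, the stated inputs call for 8 enrolled (12 with Bonferroni) on the SD of the change, or at most 14 (18) on the single-time-point SD. The plan states 25. This rests on two-sided testing (taken from 8b), equal SDs at T0 and T1, and a non-negative T0-T1 correlation; one-sided testing would lower the requirement further. How 25 arose cannot be settled from the documents.

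The error is in the safe direction, so it affects the justification rather than the conduct or validity of the trial. It should still be corrected, because it is the protocol's only sample-size statement and the 90% power it attaches to d = 1.48 is not the design's actual power at that value.

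**What to change.** Keep N = 25 and replace the derivation in 6a(iii) with the property the design has. Suggested wording: *With 25 enrolled and 10% attrition (22 completers), a two-sided paired t-test on the T0-T1 change in ALP has 90% power for a mean change of 0.73 SD of the change at alpha 0.05, or 0.84 SD at 0.05/3.* Remove the statement that 25 follows from d = 1.48 at 90% power.

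The sponsor should state which test and alpha level were used, and confirm from the earlier data which SD scales 1.48, before quoting any power at that value. If that check turns up a different calculation that does lead to 25, the section should set it out in full, including the test, SD, correlation and number of completers.

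The cost is one paragraph of protocol wording and one check of how 1.48 was standardised. Enrolment and procedures do not change.
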